Eligible patients were contacted by telephone up to 3 days prior to their appointment and assessed for enrolment. Patients were asked to suspend the night dose of carvedilol and postpone the morning dose until LSM and SSM were measured. After enrolment, patients could be excluded from the study if they failed to comply to the study regimen (last dose of carvedilol within 24 hours or related with TE protocol, namely overnight fasting), evaluated during their appointment. Informed consent were obtained from each patient included in the study.

Data Collection

For each patient, data on gender, age, aetiologies for CSPH, *D'Amico* classification, the Model for End-stage Liver Disease (MELD) scores (both MELD-Na, and MELD 3.0), Child-Pugh score, and carvedilol daily dosage were collected (22-25). For CSPH due to cirrhosis, the diagnosis of cirrhosis was based on previous biopsies or compatible clinical, biochemical, and imagiologic findings.

LSM and SSM were assessed by TE using FibroScan® 630 Expert (Echosens, Paris, France)

and values were obtained according to the recommendations of the European Federation of Societies for Ultrasound in Medicine and Biology (EFSUMB) (26). For each patient, LSM and SSM values were considered adequate if the interquartile range (IQR) was < 30% of the median value. The values were obtained, after overnight fasting, with the patient in a supine position with maximal abduction of the left arm; the probe was positioned in an intercostal space where the spleen was correctly visualized by US. LSM and SSM were expressed in kilopascal (kPa).

Data on the most recent TE in the previous 3 months and the TE performed before introduction of carvedilol were also collected through the electronic medical records of the enroled patients.

Blood chemistry tests were also performed during the appointment and results on haemoglobin, platelets, albumin, aspartate transaminase (AST), alanine transaminase (ALT), alkaline phosphatase, gamma-glutamyltransferase (GGT), total and direct bilirubin, sodium, creatinine and international normalize ratio (IQR) were collected.

Sample Size

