The sample-size calculation was based on the assumption of a SSM of 35.8 kPa during treatment and a detectable increase of 35.0% (48.3 kPa) while supressing one dose of carvedilol (1). We considered standard deviation as 19.2 kPa, an alpha of .05 and a power of .80. We also assumed that 10% of enroled patients might fulfil further exclusion criteria, by not following the study proposed regimen, totalling 33 patients needed to enrol in the study.

Data Analysis

Categorical variables were described with absolute and relative (%) frequencies and continuous variables were described with means and standard deviations (SD) when approximately normally distributed or with median an interquartile range (IQR) otherwise. Results from the SSM evaluation through TE at appointment were compared with the values measured before introduction of carvedilol and in the previous TE evaluation within 3 months, using paired t-tests. Further comparisons between SSM at appointment and within the previous 3 months were made stratifying for aetiology of portal hypertension, *D'Amico* classification, the Model MELD scores, Child-Pugh score, and carvedilol daily dosage. For the described analysis, aetiology was divided in alcoholic cirrhosis and non-alcoholic cirrhosis; in quartiles for MELD and Child-Pugh; and in above and below the median for carvedilol daily usage. The same procedure was repeated for LSM.

Data analysis was performed using R version 4.3.0 (R Foundation for Statistical Computing, Vienna, Austria). 95% confidence intervals (CI) for point estimates were calculated. P-values <.05 were considered statistically significant.

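### The 33 patients and 80% power do not follow from the stated inputs for the planned paired t-test: 24 enrolled suffice if 19.2 kPa is the SD of differences, and the type of SD is not stated

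*SAP*

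**What the plan says.** The Sample Size section of the SAP starts from the "assumption of a SSM of 35.8 kPa during treatment and a detectable increase of 35.0% (48.3 kPa) while supressing one dose of carvedilol". It continues: "We considered standard deviation as 19.2 kPa, an alpha of .05 and a power of .80". For losses it says "We also assumed that 10% of enroled patients might fulfil further exclusion criteria". The reason it gives for these losses, and the total it reaches, are as follows: "by not following the study proposed regimen, totalling 33 patients needed to enrol in the study".

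The Data Analysis section says that SSM at the appointment is "compared with the values measured before introduction of carvedilol and in the previous TE evaluation within 3 months, using paired t-tests". On inference it says "95% confidence intervals (CI) for point estimates were calculated. P-values <.05 were considered statistically significant". The comparison readings come from the same patients' records (Data Collection): "Data on the most recent TE in the previous 3 months and the TE performed before introduction of carvedilol were also collected".

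The SAP does not state the test or formula used for sizing, its sidedness, whether 19.2 kPa describes single readings or within-patient differences, any within-patient correlation, or the evaluable number before the 10% allowance. The protocol has no sample-size section.

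**The concern.** A paired t-test works on each patient's change, so the SD that sets its power is the SD of the changes. With that SD the five stated inputs should lead to the stated 33, and they do not. If 19.2 kPa is instead the spread of SSM between patients at one visit, the calculation needs a within-patient correlation, and none is given.

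This comparison is the only one that the SAP sizes. If the change in SSM is not significant, a reader will want to know how likely the study was to detect 12.5 kPa. Depending on how 19.2 kPa is read, the answer lies anywhere from about 67% to about 93%, and the SAP offers one figure, 80%, that cannot be traced. The validity of the test and its type I error are not in question.

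**Working it through.** **Inputs (SAP, Sample Size).** Mean on treatment 35.8 kPa; mean after the omitted dose 48.3 kPa (35.8 × 1.35 = 48.33, so the percentage agrees); difference δ = 48.3 − 35.8 = 12.5 kPa; SD 19.2 kPa; α = .05; power .80; loss 10%; 33 enrolled. Evaluable: 33 × 0.9 = 29.7, so 29 to 30 pairs.

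**Assumption.** The test is two-sided, inferred from the 95% confidence intervals and the .05 threshold.

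**Method.** Exact power from the noncentral t distribution with n − 1 degrees of freedom and noncentrality δ√n / SD_diff.

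**Trying to reproduce 33, with 19.2 kPa as the SD of differences**

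- Two-sided: n = 20.52, so 21 pairs (power .810; 20 pairs give .789). 21/0.9 = 23.3, so 24 enrolled. 21 × 1.10 = 23.1 also rounds up to 24.
- One-sided: n = 16.03, so 17 pairs. 17/0.9 = 18.9, so 19 enrolled.

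Neither gives 33. On this reading the two-sided power with 33 enrolled is .923 (29 pairs) to .931 (30 pairs). The difference detectable at 80% is 10.35 to 10.16 kPa; 10.35/35.8 = 28.9% and 10.16/35.8 = 28.4%, against the 35% stated.

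**With 19.2 kPa as a per-visit SD**

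SD_diff = 19.2 × √(2(1 − ρ)), where ρ is the correlation between a patient's two readings. The documents give no ρ, so a range is shown (two-sided, α = .05):

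| ρ (assumed) | SD_diff, kPa | Power, 29 pairs | Power, 30 pairs |
|---|---|---|---|
| 0 | 27.15 | .668 | .683 |
| 0.2 | 24.29 | .763 | .778 |
| 0.3 | 22.72 | .816 | .830 |
| 0.5 | 19.20 | .923 | .931 |

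Power reaches 80% when SD_diff is at most 23.19 kPa (29 pairs, ρ ≥ .270) or 23.62 kPa (30 pairs, ρ ≥ .243). A ρ of 0 is the extreme of the range, not the expected case.

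**Calculations that do return 33**

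- Two-sided paired t-test, per-visit SD: ρ of .243 to .270 (30 × 1.10 = 33) or .270 to .297 (29/0.9 = 32.2, so 33).
- One-sided t-test of two independent groups: 29.87, so 30 per group, and 30 × 1.10 = 33. This needs no correlation but is not the planned analysis.
- One-sided paired t-test, per-visit SD: ρ of about .02 to .09. The normal approximation at ρ = 0 also gets there (29.17, so 30 × 1.10 = 33).

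The documents do not show which of these, if any, was used.

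**The case against.** The strongest reply is that 33 is compatible with the planned test. The SAP quotes two visit-level means and then an SD, and never mentions an SD of change, so a per-visit reading is at least as natural. On that reading a two-sided paired t-test with ρ of about .24 to .30 gives 33 at 80% power, and the fault is an unreported input rather than a contradiction. This is correct as far as it goes. It still needs a correlation that neither document supplies, so 33 cannot be derived from what is written.

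Second, two-sided testing is inferred, and the SAP speaks of a detectable increase. One-sided, with a per-visit SD and 29 or 30 pairs, power is 78.0 or 79.3% at ρ = 0 and 81.7 or 82.9% at ρ = 0.1, so the 80% would roughly hold for any non-negative ρ. That stands and softens the lower figures in the table. It does not rescue the SD-of-differences reading, where a one-sided test needs only 19 enrolled.

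Third, the type of SD may be given in the source that the SAP cites, which was not available here. The SAP should still state it.

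Fourth, the practical consequence is limited: on the SD-of-differences reading the discrepancy is conservative, and the planned confidence intervals will carry most of the interpretation of a non-significant result. That bears on how serious the point is, not on whether it is right.

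**Conclusion.** The point holds. For the planned paired t-test, taken as two-sided, the stated inputs do not yield 33 enrolled at 80% power.

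- **SD of differences 19.2 kPa:** 24 enrolled are enough for 80%, and 33 give 92 to 93%. The mismatch with 33 does not depend on sidedness.
- **Per-visit SD 19.2 kPa:** the power of 33 enrolled depends on an unstated correlation. It is 67–68% at ρ = 0 and 92–93% at ρ = 0.5, and crosses 80% at about .24 to .27.

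The documents do not show that the study is underpowered, nor that too many patients were enrolled. They show that the 80% is wrong on one reading and unverifiable on the other. This should be fixed, but it does not undermine the analysis itself.

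**What to change.** Rewrite the Sample Size paragraph for the two-sided paired t-test of SSM at the appointment against SSM within the previous 3 months. State the sidedness, the formula, the evaluable number, and whether 19.2 kPa is the SD of within-patient differences or a per-visit SD with an assumed correlation. Replace the 80% with the power that 33 enrolled delivers. Suggested wording:

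- *If it is the SD of differences:* For a 12.5 kPa change and an SD of differences of 19.2 kPa, a two-sided paired t-test (α = .05) needs 21 evaluable pairs (24 enrolled) for 80% power; 33 enrolled (29 evaluable) give 92%.
- *If it is a per-visit SD and the correlation is unknown:* With 33 enrolled (29 evaluable), power for a 12.5 kPa change is 67% at a within-patient correlation of 0, 76% at 0.2, 82% at 0.3 and 92% at 0.5; 80% requires an SD of differences of at most 23.2 kPa.

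The cost is one recalculation and a revised paragraph; restating the power needs no extra patients. The trade-off is that, with a per-visit SD and a correlation below about .24 to .27, the restated two-sided power will fall below 80%.

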Centro Hospitalar Trás-os-Montes e Alto Douro

STATISTICAL ANALYSIS PLAN

The impact of carvedilol posology on Clinically Significant Portal Hypertension: Insights from Elastography Measurements

31 May 2023

Participants and methods

Study Design

The present study was an experimental study conducted at the Liver Unit at Centro Hospitalar de Trás-os-Montes e Alto Douro, Vila Real, Portugal. Patients with CSPH considered responders to carvedilol prescribed twice daily were included. These patients had their SSM and LSM measured through TE after suspending their second daily carvedilol intake. Results from the SSM were compared with the values measured while under treatment and before being prescribed with carvedilol. Additionally, comparisons for under treatment with carvedilol and 24-hour suspension were stratified according to carvedilol daily dosage, *D'Amico* classification, the Model for End-stage Liver Disease (MELD) scores, Child-Pugh score, and aetiologies for PH. The same procedure was repeated for the results of LSM. This study was approved by the clinical research ethics committee of Centro Hospitalar de Trás-os-Montes e Alto Douro, in accordance with the 1975 Declaration of Helsinki declaration.

Participants

All patients over 18 years of age, followed at the Liver Unit at Centro Hospitalar de Trás-os-Montes e Alto Douro, Vila Real, Portugal for CSPH (defined as a LSM \geq 25 kPa or SSM over 45kPa prior to introduction of carvedilol) were eligible. Patients were excluded from the study if they were non-responders to NSBB (defined as a reduction of their SSM of less than 10%), were under treatment with any NSBB other than carvedilol, had a dosing regimen other than twice daily, had not been performed a SSM or LSM through TE while under treatment within 3 months prior to the beginning of the study, were obese (body mass index (BMI) $>$ 30 m/kg²), had contraindications to NSBB use, presented portal venous thrombosis or refused to participate in the study.

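### The pre-carvedilol SSM is biased upward by the entry and responder rules and has no time window, so a plain paired t-test against it can show a retained drug effect that is not there

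*SAP*

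**What the plan says.** SAP, Data Analysis: appointment SSM is "compared with the values measured before introduction of carvedilol and in the previous TE evaluation within 3 months, using paired t-tests". The procedure is repeated for LSM, 95% CIs are planned for point estimates, and P<.05 counts as significant. No comparison is named as primary.

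SAP, Data Collection: "Data on the most recent TE in the previous 3 months and the TE performed before introduction of carvedilol were also collected" from the medical records. The 3-month limit applies to the on-treatment TE. No limit is given for the pre-carvedilol TE.

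SAP, Participants (and the protocol's inclusion and exclusion criteria): entry requires LSM ≥25 kPa or "SSM over 45kPa prior to introduction of carvedilol". Patients are excluded if they were "non-responders to NSBB (defined as a reduction of their SSM of less than 10" per cent). Neither document says which TE readings define that reduction.

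SAP, Sample Size: the calculation rests on the "assumption of a SSM of 35.8 kPa during treatment" and "a detectable increase of 35.0% (48.3 kPa) while supressing one dose of carvedilol". That is the acute contrast. The pre-carvedilol value plays no part in it.

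Neither document describes a control group, a repeat pre-treatment TE, or an adjustment for regression to the mean or elapsed time.

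**The concern.** A paired t-test takes the mean difference as an effect. Here the earlier member of the pair was chosen partly for being high, and was kept only if a later reading was lower. Its measurement error is therefore positive on average among the patients analysed. The appointment reading is new and carries no such selected error. Appointment SSM is expected to lie below pre-carvedilol SSM even if all drug effect has gone.

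The study asks what happens to stiffness when a dose is omitted. An appointment value significantly below the pre-carvedilol value would naturally suggest that some effect survives the omission, and selection alone can produce that pattern.

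The open interval is a separate problem. Any change in the liver disease or its cause between the pre-carvedilol TE and the appointment enters the difference. Improvement mimics a retained effect and worsening hides one.

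**Working it through.** **1. Inputs from the SAP.** Acute contrast: 35.8 × 1.35 = 48.3 kPa, a difference of 12.5 kPa; SD 19.2 kPa. Enrolment of 33 less 10% gives 33 × 0.9 = 29.7, so n = 30 evaluable. (A one-sided, unpaired, per-group formula returns 30, and 30 × 1.1 = 33. That is not the planned paired test, but only n = 30 is used here.) If the value after one omitted dose stood for the untreated value, the on-treatment drop would be 1 − 35.8/48.3 = 25.9%.

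**2. Assumptions, because the documents give no figures.** True untreated SSM T is lognormal, mean 45 kPa, CV 0.54. Each reading has independent log error with SD σ = 0.10–0.20. The true on-treatment drop d is 20–30%. Half of patients qualify through LSM regardless of SSM. The 10% fall is measured from the pre-carvedilol SSM to an on-treatment SSM.

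**3. Model with no drug effect left at the appointment.**
- Pre = T·exp(ε0); On = T(1 − d)·exp(ε1); App = T·exp(ε2).
- Keep a patient if (Pre > 45 or LSM route) and On ≤ 0.9·Pre.
- Two-sided .05 paired t-test of App against Pre, n = 30; count significant results with App lower.

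**4. Hand check, responder rule only.** A patient is kept when ε0 − ε1 ≥ ln[(1 − d)/0.9]. With s = σ√2 and z = ln[(1 − d)/0.9]/s, the mean of ε0 among those kept is (s/2)·φ(z)/[1 − Φ(z)].
- σ = 0.10, d = 20%: s = 0.141, z = −0.83, mean ε0 = 0.025; 45 × 0.025 ≈ 1.1 kPa (simulated 1.1).
- σ = 0.20, d = 20%: s = 0.283, z = −0.42, mean ε0 = 0.078; 45 × 0.078 ≈ 3.5 kPa (simulated 3.5).

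**5. Both rules, half entering through LSM (simulated).**

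| σ | Drop d | Mean App − Pre (kPa) | False retained effect |
|---|---|---|---|
| 0.10 | 30% | −0.5 | 5% |
| 0.10 | 20% | −1.5 | 17% |
| 0.15 | 30% | −1.6 | 11% |
| 0.15 | 20% | −2.9 | 27% |
| 0.20 | 30% | −3.0 | 18% |
| 0.20 | 20% | −4.6 | 35–36% |

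The nominal rate in this direction is 2.5%. Without selection the same model gives a mean difference of 0.0 kPa and 2.2–2.4%.

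**6. A second model.** Additive errors, the SAP's SD of 19.2 kPa, an assumed pre-carvedilol mean of 60 kPa, both rules, half entering through LSM:

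| Test-retest ICC | 25.9% drop: kPa, false rate | 15% drop: kPa, false rate |
|---|---|---|
| 0.70 | −3.5, 25% | −5.2, 51% |
| 0.80 | −2.4, 19% | −4.0, 46% |
| 0.90 | −1.1, 10% | −2.5, 37% |
| 0.95 | −0.5, 6% | −1.5, 29% |

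In this model, over assumed means of 48.3 and 60 kPa, the entry threshold alone with its LSM route gives only −0.15 to −1.5 kPa and 3–8%. The responder rule drives most of the bias.

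**7. Open interval.** In the step 3 model, with every patient's appointment value shifted by 10% for non-drug reasons: a 10% improvement gives a false retained effect in 82% to over 99% of studies; a 10% worsening gives 0–2%, with significance in the opposite direction in 3–83%. The size of shift is arbitrary. The runs show only that the result follows the drift.

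**8. The acute comparison.** If the TE within 3 months is also the one that defined response, that reading is selected to be low. App − On is then biased towards apparent loss of effect by about +0.3 to +3.9 kPa. The upper end applies if every patient entered on SSM >45; with half entering through LSM, a rerun topped out at about +3.3. The second model gives +0.3 to +5.0 kPa over drops of 15% and 25.9%.

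**The case against.** **The plan already centres on the acute contrast.** The sample size and all stratified analyses use appointment against on-treatment SSM. A reader might infer that the SAP gives the pre-carvedilol test confirmatory standing. It does not: it names no primary or confirmatory comparison. What stands is that it applies the same test and threshold to both and never states the role of the second.

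**No rule says how the result will be read.** Neither document says that a value below the pre-carvedilol one will be taken as persisting effect. The protocol's stated interest is whether twice-daily dosing keeps the effect better, and a false retained effect would work against that. This is fair. It limits the harm but does not make the test valid, and stating the interpretation in advance costs one sentence.

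**The size rests on assumptions.** This is also fair. The documents give neither SSM reliability nor the pre-carvedilol mean. Requiring SSM >45 kPa in everyone would raise the top of the range to about 54%, but the criterion is LSM or SSM, so that figure does not describe this population.

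**Drift.** A reader might infer from the missing window that a false retained effect is close to certain. That needs an assumed improvement of about 10% in every patient, for which the documents give no support. Worsening acts the other way.

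**The acute comparison as a clean alternative.** A reader might infer that dropping the pre-carvedilol test leaves an unbiased one. The documents do not establish this, because the readings that define response are not named.

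**Conclusion.** The concern holds as a bias in one of the two planned tests. With no drug effect left, selection alone puts appointment SSM about 0.5–4.6 kPa below the pre-carvedilol value and gives a false retained effect in about 5–36% of studies, against 2.5% nominal. This rests on n = 30 from the SAP and on the assumed error, drop and LSM share in step 2 of the working. It also assumes that the responder rule is measured from the pre-carvedilol SSM. The rate approaches nominal if SSM is very reliable and the drop is large, and it is higher if the drop is smaller (29–51% at 15% in the second model).

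The missing window adds an error of unknown size and direction, for which no figure is claimed. The procedure is repeated for LSM, but no size was worked out there.

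The documents do not support saying that the study's main conclusion is invalid: the contrast behind the sample size is the other one. That contrast needs its own caveat if the 3-month TE defined response.

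**What to change.** In SAP, Data Analysis:

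1. Report the pre-carvedilol comparison descriptively for SSM and LSM: the values, the paired difference with 95% CI, and the time since that TE. State that it will not be used to claim that carvedilol effect is kept or lost.
2. Take the acute-effect conclusion from appointment against on-treatment SSM, the contrast used for the sample size.
3. State which TE readings define the 10% responder rule. If the TE within 3 months is one of them, say that the acute comparison is biased towards apparent loss of effect. Where the records hold another on-treatment TE, add a sensitivity analysis using one that did not define response.

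Cost: SAP wording, one date per patient from records already being read, and a further look at those records for the sensitivity analysis. No extra visits or patients are needed and the sample-size contrast is unchanged. The downside is the loss of a significance claim for a secondary comparison.

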**Introduction / Theoretical foundations:**

Transitory elastography is a non-invasive diagnostic method that has been used for the diagnosis and follow-up of patients with clinically significant portal hypertension (CSPH). In this context, the use of targeted therapies to reduce complications resulting from this finding plays a crucial role in managing these patients.

Carvedilol is a non-selective beta-blocker currently considered the first-line drug for treating patients with CSPH. Regarding its pharmacokinetic characteristics, its half-life is approximately 7 to 10 hours. However, there is still a debate in dosing regimen, specially regarding dose interval, with a potential lower bioavailability in once daily regimens

Nevertheless, although the dosing frequency may influence portal pressure and cardiac function, the direct impact on the value of splenic and liver elastography is not fully understood, and there are no studies directly comparing and evalutiang this topic. Therefore, focused studies assessing the impacto f once-daily vs twice daily dosing regimens become essential to improving clinical practice.

**Objectives:** To assess the acute effects of carvedilol posology in patients with clinically significant portal hypertension (CSPH), as a surrogate marker of bioavailability.

**Study design:** experimental study including patients with CSPH considered responders to carvedilol prescribed twice daily. These patients had their spleen stiffness measurement (SSM) and liver stiffness measurement (LSM) measured through elastography after suspending their second daily carvedilol intake. Results from the SSM were compared with the values measured while under treatment and before being prescribed with carvedilol. Additionally, comparisons for under treatment with carvedilol and 24-hour suspension were stratified according to carvedilol daily dosage, D'Amico classification, the Model for End-stage Liver Disease (MELD) scores, Child-Pugh score, and aetiologies for portal hypertension. The same procedure was repeated for the results of LSM.

**Target population:** patients with CSPH considered responders to carvedilol prescribed twice daily

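### The stratified SSM and LSM comparisons come with a p<.05 threshold but no planned estimate of how the change differs between strata; for SSM quartiles, mixed significance is likely even under a uniform effect if the SD of change is about 10 to 27 kPa

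*SAP*

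**What the plan says.** The SAP's Data Analysis section compares SSM at the appointment with the value before carvedilol and with the value "in the previous TE evaluation within 3 months, using paired t-tests". It then adds: "Further comparisons between SSM at appointment and within the previous 3 months were made stratifying for aetiology of portal hypertension", with D'Amico class, MELD, Child-Pugh and daily dose as the other factors. Aetiology is split in two, and the remaining cut points given are "in quartiles for MELD and Child-Pugh; and in above and below the median for carvedilol daily usage". No grouping is given for D'Amico class. The section then states: "The same procedure was repeated for LSM".

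The stratification is also in the protocol's Study design paragraph ("Additionally, comparisons for under treatment with carvedilol and 24-hour suspension were stratified according to carvedilol daily dosage") and in the SAP's Study Design section, so it is a planned analysis. The paired t-test is named for the overall comparison, and its use inside strata is implied.

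Data Analysis closes with 95% intervals for point estimates and a significance threshold of p<.05. Neither document plans an interaction test, a between-stratum difference with its interval, or a regression on a score or on dose. Neither calls these comparisons exploratory.

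**The concern.** The natural reason to stratify by severity, aetiology or dose is to learn whether the SSM rise after a missed dose depends on them. That is a question about the difference between strata. A paired test inside one stratum asks only whether the change in that stratum differs from zero, and in a group of 7 or 8 the answer depends heavily on sample size and chance.

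If the stratum p-values are what gets reported, some quartiles may be significant and others not although every patient responds alike. A reader could then conclude that the missed dose matters only at certain levels of liver disease. The quantity that would support or refute that conclusion is not among the planned outputs.

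**Working it through.** **Inputs.** From the SAP's Sample Size section: "assumption of a SSM of 35.8 kPa during treatment and a detectable increase of 35.0% (48.3 kPa" (closing bracket omitted) and "We considered standard deviation as 19.2 kPa, an alpha of .05 and a power of .80". The rise is 48.3 - 35.8 = 12.5 kPa. Enrolment is 33 with a 10% allowance, so 33 x 0.9 = 29.7, about 30 evaluable. Even quartiles hold 8, 8, 7 and 7; even halves hold 15.

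**The plan's own figure.** A one-sided two-sample formula gives 2 x [19.2 x (1.645 + 0.842)/12.5]^2 = 29.2, rounded up to 30, and 30 x 1.1 = 33. A two-sided paired t-test with 19.2 as the SD of change needs 21 evaluable, and 21/0.9 = 23.3, so 24 enrolled. The SAP does not say what 19.2 kPa refers to or whether tests are two-sided. I therefore assume two-sided tests and show a range of SDs. The value 23.6 kPa is an assumption: it is the SD of change at which a two-sided paired test on 30 patients has 80% power. If 19.2 is the SD of a single measurement, the SD of change is 19.2 x sqrt(2(1 - r)), with the within-patient correlation r assumed.

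**Power in a stratum.** Noncentral t with n - 1 degrees of freedom and noncentrality (12.5/SD) x sqrt(n).

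**Mixed significance in a quartile factor when every patient has the same rise.** P(mixed) = 1 - P(all four significant) - P(none significant).

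- SD 19.2: power is 0.306 (n=7) and 0.357 (n=8). All four: 0.306^2 x 0.357^2 = 0.012. None: 0.694^2 x 0.643^2 = 0.199. Mixed: 0.789. A simulation of 200,000 trials gave 0.791.
- SD 23.6: power is 0.220 and 0.254. All four: 0.003. None: 0.338. Mixed: 0.659, also 0.659 by simulation.

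| SD of change (kPa) | r, if 19.2 is a single-measurement SD | Power, n=7 / n=8 | Quartile factor mixed |
|---|---|---|---|
| 27.2 | 0 | 18% / 20% | 57% |
| 23.6 | 0.24 | 22% / 25% | 66% |
| 19.2 | 0.5 | 31% / 36% | 79% |
| 14.9 | 0.7 | 46% / 53% | 88% |
| 12.1 | 0.8 | 63% / 71% | 79% |
| 10.5 | 0.85 | 75% / 82% | 62% |
| 9.8 | 0.87 | 80% / 87% | 51% |
| 8.6 | 0.9 | 89% / 94% | 30% |

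**Uneven groups.** Tied scores, likely for Child-Pugh, would make the groups unequal. With assumed sizes of 12, 8, 6 and 4 the mixed figure is 81% at SD 19.2 and 67% at 23.6.

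**Two-way split.** For even halves of 15, P(mixed) = 2p(1 - p). At SD 19.2 this is 2 x 0.650 x 0.350 = 0.455, and at 23.6 it is 2 x 0.480 x 0.520 = 0.499. Neither exceeds one half.

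**LSM.** The documents give no LSM effect or SD, so no figure can be calculated.

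**The case against.** The strongest reply is that the harm is hypothetical. No passage says stratum p-values will be compared or ties a conclusion to a stratum. The protocol's objective states no effect-modification hypothesis, the strata are introduced as additional comparisons, and the sample size rests on the overall SSM change. The planned 95% intervals would let a careful reader work out a between-stratum difference by hand. All of that stands, and it limits the point to a recommendation about analysis and reporting. It does not supply the missing estimate or the exploratory label.

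A second reply also stands: the mixing figures depend on an SD of change that the SAP does not clearly give. At 8.6 kPa most trials would show all four quartiles significant. The 23.6 kPa case is inferred; the enrolment of 33 can be reproduced by another formula that does not imply it.

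A reader might infer three stronger things:

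- **That the authors intend to claim subgroup differences from stratum p-values.** The documents do not say so.
- **That mixed results would usually look like a severity gradient.** A pattern with exactly one switch along the ordered quartiles arises in 35% of trials at SD 19.2 and 30% at 23.6, so usually it would not.
- **That every stratified comparison has the problem to the same degree.** The figures do not extend to a single even two-way split or to LSM.

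Finally, the replacement analysis has little power. That is true. But a wide interval shows how little the strata can tell apart, which a list of stratum p-values does not.

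**Conclusion.** The point holds in a limited form. The plan repeats the paired comparison within strata, gives p<.05 as the only threshold, and does not estimate how the change differs between strata. As written it cannot show whether the effect varies with severity, aetiology or dose.

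For SSM quartiles under a uniform 12.5 kPa rise, mixed significance is expected in 79% of trials at an SD of change of 19.2 kPa and in 66% at an assumed 23.6 kPa. It is the majority result for SDs from about 10 kPa up to the 27 kPa examined. This rests on about 30 evaluable patients, even quartiles and two-sided tests. The overall SSM comparison is untouched. The change should be made because it is cheap and supplies the relevant quantity; the main result does not depend on it.

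**What to change.** State in the SAP that no conclusion will be drawn from within-stratum p-values, and present stratum means with 95% intervals as descriptive only. For SSM and for LSM, model the paired change (appointment minus on-treatment) on each factor and report, labelled exploratory and with a 95% CI:

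- the slope per point of one pre-named MELD score (the SAP collects both MELD-Na and MELD 3.0 and does not say which defines the quartiles);
- the slope per Child-Pugh point;
- the slope per unit of daily dose, or at or below the median versus above it;
- the difference between alcohol-related and all other aetiologies;
- for D'Amico class, the slope per stage or a single pre-named contrast.

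**Cost.** SAP wording and a few lines of R, with no new data. The intervals will be wide. For halves of 15 the 95% half-width is 2.048 x SD x sqrt(2/15), which is 14.4 kPa at SD 19.2 and 17.7 kPa at 23.6, both larger than the planned 12.5 kPa rise. Power for a 12.5 kPa difference between halves is about 41% and 29%. A null result must therefore not be read as no difference. The slopes assume linearity. Five unadjusted terms per outcome would carry a false-positive risk of 1 - 0.95^5 = 0.226 if independent, which is why the exploratory label is needed.
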